#### **4.4.1.3 Supplementary analyses**

**The key secondary endpoint**, change from baseline to Week 24 for Bilateral NPS, NC symptom severity score and LMK score will be analyzed using the mITT population and the following methodologies for intercurrent events:

- **Treatment policy strategy:** Discontinuing the treatment prematurely (Participants who did not take rescue medications or undergo surgery): all data collected after treatment discontinuation will be used in the analysis
- **Hypothetical strategy:** Taking rescue medications or undergo surgery for CRSwNP prior to Week 24: data will be set to missing after the medication usage, and the participant's worst postbaseline value on or before the time of the medication usage or surgery will be used to impute the missing Week 24 value (for participants whose postbaseline values are all missing, the baseline will be used to impute).

#### **4.4.2 Supportive secondary endpoints**

- Change from baseline at Week 24: Total symptom score (TSS)
- Change from baseline at Week 24: Loss of smell severity score
- Visual analogue scale for rhinosinusitis

##### **4.4.2.1 Definition of endpoints**

###### Change from baseline at Week 24 in TSS and Loss of smell severity score

TSS is a composite score (ranging between 0 and 9) consisting of the sum of the following symptoms assessed daily in the morning: nasal congestion/obstruction, decreased/loss of sense of smell, and rhinorrhea (average of the non-missing anterior/posterior nasal discharge). At least 2 symptoms scores must be reported to calculate the TSS, otherwise the score will remain missing.

The symptoms scores at baseline and changes from baseline will be calculated using the same approach as for NC as described in Section 4.4.1.1. Baseline is defined as the average of the non-missing 7 days prior to enrollment and requires  $\geq 4$  responses. Timepoints will be evaluated using the average symptom severity from the most recent 28 days before each scheduled visit. Participants with fewer than 28 days in between visits will use data from one day after the previous visit through the day of the current visit. At least 50% of days (with a maximum of 28) must be non-missing in order to calculate the average symptom severity.

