8.1.4 Nasal symptom diary: Disease specific daily symptom assessment and total symptom score

On a daily basis from Visit 1 and throughout the study, the participant will use a diary to:

- Respond to the morning individual rhinosinusitis symptom questions using a 0 to 3 categorical scale (where 0 = no symptoms, 1 = mild symptoms, 2 = moderate symptoms, and 3 = severe symptoms) (11):
 - Congestion and/or obstruction
 - Loss of sense of smell
 - Anterior rhinorrhea (runny nose)
 - Posterior rhinorrhea (postnasal drip)

The total symptom score (TSS) is a composite score (ranging between 0 and 9) consisting of the sum of the following symptoms assessed daily in the morning: nasal congestion/obstruction, decreased/loss of sense of smell, and rhinorrhea (average of anterior/posterior nasal discharge).

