#### Change from baseline to Week 24 in NC symptom severity score:

On a daily basis from Visit 1 and throughout the study, the participant will use a diary to respond to the morning individual rhinosinusitis symptom questions evaluating symptom severity over the past 24 hours using a 0 to 3 categorical scale (where 0 = no symptoms, 1 = mild symptoms, 2 = moderate symptoms, and 3 = severe symptoms) as described in Table 6 below.

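### The SAP lets the daily TSS be summed from 2 symptom scores with no stated rescaling, so an absent congestion, smell or whole rhinorrhea component counts as 0

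*SAP*

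**What the plan says.** Both documents define the TSS as an unweighted sum. Protocol 8.1.4: "The total symptom score (TSS) is a composite score (ranging between 0 and 9) consisting of the sum of the following symptoms". SAP 4.4.2.1 has the same construction: "TSS is a composite score (ranging between 0 and 9) consisting of the sum of the following symptoms assessed daily in the morning". The three components are congestion/obstruction, loss of smell, and rhinorrhea. Each diary item is scored "using a 0 to 3 categorical scale" (SAP 4.4.1.1).

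The protocol has no rule for an incomplete diary day. The SAP adds two:

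- Within rhinorrhea, the component is entered as "rhinorrhea (average of the non-missing anterior/posterior nasal discharge", so one of the two discharge items is enough.
- For the sum itself: "At least 2 symptoms scores must be reported to calculate the TSS, otherwise the score will remain missing".

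Nothing says what happens to the sum when a component is absent but the minimum is met. The SAP also does not say whether the minimum counts the three components or the four diary items.

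Daily values are then averaged. "Timepoints will be evaluated using the average symptom severity from the most recent 28 days before each scheduled visit", and "At least 50% of days (with a maximum of 28) must be non-missing in order to calculate the average symptom severity". Baseline is the mean over the 7 days before enrollment, with at least 4 responses.

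**The concern.** A minimum of 2 scores has a purpose only if some days will be incomplete. On such a day a plain sum of what was reported is no longer on the 0-9 scale, because the absent component adds nothing. That is the same as recording that the symptom was not there. Complete and incomplete days are then averaged together as if they were comparable.

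No later step repairs this. The worst-observation and multiple-imputation steps in SAP 4.4.1.2 work on visit values, so a window mean that includes incomplete days is treated as observed. The by-visit summaries in SAP 4.5.2.3 use no imputation. The mITT supplementary analysis in SAP 4.4.1.3 covers NPS, congestion and Lund-Mackay, not TSS. There is no control arm in which the same artefact would appear and could be subtracted.

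The rule also produces an inconsistency. If smell is skipped on more than half the days of a window, the loss-of-smell score is missing under the 50% rule. The TSS for the same window, which needs that item, can still stand as observed.

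At stake is the change from baseline in TSS, an other secondary endpoint at Week 24 and an exploratory one at Week 52.

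**Working it through.** **Inputs.** Items are scored 0 to 3 (SAP 4.4.1.1, Table 6). TSS = congestion + smell + mean of the reported anterior and posterior items (SAP 4.4.2.1). Windows are 28 days after baseline and 7 days at baseline (SAP 4.4.2.1). The share of days with an absent component is not in either document, so the rates below are assumptions.

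**1. Reproduce the stated range.** Minimum 0 + 0 + 0 = 0; maximum 3 + 3 + 3 = 9. All 256 combinations of four 0-3 items give 0 to 9, as stated.

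**2. One component absent, sum of the rest.** Maximum 3 + 3 = 6. With every component at 2, the full score is 2 + 2 + 2 = 6 and the incomplete score is 2 + 2 = 4, a shortfall of 2. In general the shortfall equals the absent component's true score.

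**3. Direction by item, over the 256 combinations.**

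| Absent | Day's TSS lower | Unchanged | Higher | Mean difference |
|---|---|---|---|---|
| Congestion | 192 | 64 | 0 | -1.5 |
| Smell | 192 | 64 | 0 | -1.5 |
| Both rhinorrhea items | 240 | 16 | 0 | -1.5 |
| One rhinorrhea item only | 96 | 64 | 96 | 0 |

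The first three can never raise the score. A single missing rhinorrhea item has no systematic direction. The mean column weights all combinations equally; it shows direction and is not a forecast for this trial.

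**4. Shift in a post-baseline window mean, symptoms unchanged.** Shift = -(true score of the absent component) x (fraction of days affected).

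| Assumed fraction of days | Component scored 2 | Component scored 3 |
|---|---|---|
| 10% | -0.2 | -0.3 |
| 25% (7 of 28) | -0.5 | -0.75 |
| 50% (14 of 28) | -1.0 | -1.5 |

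A single affected day of 28 gives -2/28 = -0.07. If the component scored 2 were absent every day, the shift would be -2.0.

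**5. The same gap at baseline.** One affected day among 7 lowers baseline by 2/7 = 0.29. Change is follow-up minus baseline, so this makes improvement look 0.29 smaller. Per affected day, a baseline gap weighs four times as much as one in a full 28-day window (28/7 = 4).

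**6. The two readings of the minimum.** If 2 of 3 components are needed, a day with only the two rhinorrhea items has one component and is missing. If 2 of 4 diary items are enough, that day counts, with a maximum of 3.

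**7. Check of proration.** Prorated TSS = 3 x mean of the available components. With smell absent, 2/2/2 gives 3 x (2 + 2)/2 = 6 and 3/3/3 gives 3 x (3 + 3)/2 = 9, so both shortfalls disappear. Proration is exact only when the absent component equals the mean of the others. With congestion 1, smell 3 and rhinorrhea 1 (true score 5), losing smell gives 3 prorated and 2 as a plain sum. With 2, 0 and 2 (true score 4), it gives 6 prorated and 4 as a plain sum. Its error can go either way, whereas the plain sum can only go down.

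**The case against.** The strongest reply is that the SAP does not say an absent component is scored 0. It is silent, and a programmer might prorate. That is fair as far as it goes, but the text gives an operation (a sum) and a condition for carrying it out (2 scores). Following both literally gives the shortfall. The SAP states a missing-item rule inside rhinorrhea and none for the sum, so proration would have to be added by the programmer.

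The other limits stand:

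- A reader might infer that any skipped diary item lowers the TSS. The documents do not support this: a lone missing rhinorrhea item is averaged out by the SAP's own rule.
- A reader might infer that the results will be biased toward improvement. That needs components to be missing more after baseline than before, allowing for the greater weight of each baseline day. Nothing shows this. Protocol 8.1.2 has the site check the diary at every visit, and the baseline requirement of 4 mornings in 7 concerns completed mornings, not items. The documents do not even say whether the diary lets a participant leave one item blank.
- The day capped at 3 depends on the 2-of-4-items reading. Since the SAP sums three symptoms, 2 of 3 components is the more natural reading.
- The trial tests no hypothesis. Its similarity judgement rests on the NPS responder proportion, which does not use the diary. Congestion and loss of smell are also analysed separately, so a marked TSS artefact could be noticed against them.

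**Conclusion.** The derivation rule is wrong as written. An absent congestion score, smell score or whole rhinorrhea component acts as a score of 0, the day's ceiling falls from 9 to 6, and the day's TSS drops by the true value of what is absent.

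The size over a window depends on item completeness, which the documents do not give. At assumed rates of 10%, 25% and 50% of days, with the absent component worth 2, the 28-day mean shifts by -0.2, -0.5 and -1.0. With few incomplete days the effect is negligible. Post-baseline gaps flatter the treatment and baseline gaps do the reverse, so a net bias toward improvement is possible but not shown.

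The consequence is confined to TSS. The primary endpoint, the three key secondary endpoints, the separate loss-of-smell score and the VAS are unaffected. The point deserves correction because the endpoint is named, the error has a fixed direction on each affected day, and the repair is nearly free.

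**What to change.** Amend SAP 4.4.2.1 in two respects.

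1. State that the minimum is 2 of the 3 components, not 2 of the 4 diary items. Rhinorrhea counts as present when at least one of its two items is reported.
2. Either prorate the daily TSS as 3 x the mean of the available components, or set the day's TSS to missing unless all three components are present.

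Proration keeps more days but assumes the absent component resembles the other two. Requiring all three avoids that assumption but loses some diary days, and a few more windows may fall below the 50% threshold and pass to the imputation already planned. Either choice removes the built-in downward error. The rule should apply alike to the baseline week and later windows, which the SAP's single TSS definition already implies.

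The cost is a sentence or two in the SAP and one line of derivation code. No data collection changes.

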1.2 SCHEMA

Figure 1 - Graphical study design

Abbreviations: D: day; EOS: end of study, EOT: end of treatment; q2w: every 2 weeks; q4w: every 4 weeks; V: visit.

Procedure	D-28 to D-14	Intervention Period							
		W0 D1	W2 D15 (±3 days)	W4 D29 (±3 days)	W8 D57 (±3 days)	W16 D113 (±3 days)	W24 D169 (±3 days)	W40 D281 (±3 days)	W52 D364 (±3 days) EOT/EOS
Visit	V1 (Screening)	V2	V3	V4	V5	V6	V7	V8	V9
CT scan	X ^e						X		X
Nasal Symptom Diary ^f (includes nasal congestion, loss of smell, anterior and posterior rhinorrhea; TSS derived from these 4 items)		←————— daily diary —————→							
VAS for rhinosinusitis		X	X	X	X	X	X	X	X
Vital signs ^g	X	X			X	X	X	X	X
12-Lead ECG (local reading)	X								
AE review		←—————							
SAE review		←—————							
Laboratory assessments (including hematology, biochemistry, and urinalysis) ^h	X	X			X		X		X
Hepatitis B and C; HIV testing; TB testing ⁱ	X					X ^j	X ^j	X ^j	X ^j
Pregnancy test (WOCBP only) ^k	X	X		X	X	X (W12, 16)	X (W20, 24)	X (W28, 32, 36, 40)	X (W44, 48, 52)

Abbreviations: AE: adverse event; CT: computerized tomography; D: day; e-CRF: electronic case report form; ECG: electrocardiogram; EOS: end of study; EOT: end of treatment; HBcAb: hepatitis B core antibody; HBsAb: hepatitis B surface antibody; HBsAg: hepatitis B surface antigen; HCV Ab: hepatitis C virus antibody; HIV: human immunodeficiency virus; IgM: immunoglobulin M; IGAR: Interferon-gamma release assay; IMP: investigational medicinal product; IVRS/IWRS: interactive voice/web response system; MRI: magnetic resonance image; NE: nasal endoscopy; NERD: non-steroid anti-inflammatory drug exacerbated respiratory disease; NP: nasal polyposis; NPS: nasal polyp score; q2w: every 2 weeks; q4w: every 4 weeks; SAE: serious adverse event; SCS: systemic corticosteroids; TB: tuberculosis; TSS: total symptom score; V: visit; VAS: visual analogue scale; W: week; WOCBP: women of childbearing potential.

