If the participant (or caregiver) is unable or unwilling to administer IMP, arrangements must be made for qualified site personnel and/or healthcare professionals to administer IMP for the doses that are not scheduled to be given at the study site. If the participant or caregiver(s) do not become comfortable with injecting the IMP at home or if the Investigator determines that participant (or caregiver) administering an injection at home is not appropriate, injections can be performed at the site by way of unscheduled visits.

Subcutaneous injection sites should be alternated among the 4 quadrants of the abdomen (avoiding the navel and waist areas), the upper thighs, and the upper arms, such that the same site is not injected twice consecutively. Injection in the upper arms can be done only by a trained person (caregiver trained by Investigator or designee) or health care professional but not the participants themselves.

Post-trial access to IMP will not be provided.

Table 2 - Overview of study interventions administered

Arm name	Dupilumab
Intervention name	Dupilumab 300 mg
Type	Biological
Dose formulation	A 150 mg/mL dupilumab solution in a prefilled syringe to deliver 300 mg in 2 mL
Unit dose strength(s)	300 mg
Dosage level(s)	300 mg q2w or q4w ±3 days
Route of administration	Subcutaneous
Use	Experimental
IMP or NIMP	IMP
Packaging and labeling	One glass prefilled syringe packed in a participant kit box. Both the glass prefilled syringe and the box will be labeled as required per country requirement.
Former names	Dupixent
Abbreviation: IMP: investigational medicinal product; NIMP: noninvestigational medicinal product; q2w: every 2 weeks; q4w: every 4 weeks	

The IMP may be supplied at the site or from the Investigator, site, or Sponsor to the participant via a Sponsor-approved courier company where allowed by local regulations and agreed upon by the participant.

Detailed instructions for transport, storage, preparation, and administration of IMP are provided to the participants. For doses that are not given at the study site, participants will complete a paper dosing diary to document compliance with self-injection (or caregiver injection) of IMP, location of injection, and any symptoms. The diary will be kept as source data in the participant's study file.

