8.1.2 Nasal congestion/obstruction symptom severity score

Nasal congestion/obstruction will be assessed by the participant using a diary on a daily basis from Visit 1 and throughout the study, on a 0 to 3 categorical scale (where 0 = no symptoms, 1 = mild symptoms, 2 = moderate symptoms and 3 = severe symptoms) (7):

Nasal congestion/obstruction will be scored as a reflective score (evaluation of symptom severity over the past 24 hours) by the participants (Table 4).

Table 4 - Nasal congestion/obstruction symptom severity score

Scale	Symptoms
0	No symptoms
1	Mild symptoms (symptoms clearly present, but minimal awareness and easily tolerated)
2	Moderate symptoms (definite awareness of symptoms that is bothersome but tolerable)
3	Severe symptoms (symptoms that are hard to tolerate, cause interference with activities or daily living)

The diary will be dispensed at Visit 1, and the diary will be checked by the study site at each visit.

A NC symptom severity score ≥ 2 at Visit 1 and a weekly average severity greater than 1 at the time of enrollment (Visit 2) are required and will be provided to the site to determine participant eligibility. The participant must have 4 or more measurements collected within 7 days prior to enrollment; the baseline will be the average of these measurements (E 24).

For the baseline to EOT/EOS analysis, the average of the symptom severity scores from the most recent 4 weeks before a scheduled visit will be used.

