**Table 6 - Symptom severity score**

Scale	Symptom severity description
0	No symptoms
1	Mild symptoms (symptoms clearly present, but minimal awareness and easily tolerated)
2	Moderate symptoms (definite awareness of symptoms that is bothersome but tolerable)
3	Severe symptoms (symptoms that are hard to tolerate, cause interference with activities or daily living)

A NC symptom severity score  $\geq 2$  at Visit 1 and a weekly average severity  $> 1$  at the time of enrollment (Visit 2) are required and will be provided to the site to determine participant eligibility. The participant must have 4 or more measurements collected within 7 days prior to enrollment; the baseline will be the average of the non-missing measurements.

For the baseline to EOT/EOS analysis, the average of the symptom severity scores from the most recent 4 weeks before a scheduled visit will be used.

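### The congestion diary window is not cut at first dose, so about half of the Week 2 average is pre-treatment, and its rules differ from those for TSS and smell

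*SAP*

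**What the plan says.** For NC, protocol 8.1.2 states: "For the baseline to EOT/EOS analysis, the average of the symptom severity scores from the most recent 4 weeks before a scheduled visit will be" taken. SAP 4.4.1.1 repeats this. Neither place shortens the window near first dose, excludes screening entries, or sets a minimum number of post-baseline entries. A minimum (4 of 7 days) is given for baseline only.

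For TSS and loss of smell, SAP 4.4.2.1 says that the scores are "calculated using the same approach as for NC as described in Section 4.4.1.1". It then sets out rules that 4.4.1.1 does not contain:

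- Window: "Timepoints will be evaluated using the average symptom severity from the most recent 28 days before each scheduled visit".
- Truncation: "Participants with fewer than 28 days in between visits will use data from one day after the previous visit through the day of the current" one.
- Completeness: "At least 50% of days (with a maximum of 28) must be non-missing in order to calculate the average symptom severity".

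The window sentence names scheduled visits; the truncation sentence does not. Unscheduled visits are foreseen. Under protocol 6.1, if home dosing is unwanted or unsuitable, "injections can be performed at the site by way of unscheduled visits", and protocol 4.1 allows an unscheduled visit for deterioration. The unscheduled-visit paragraph in SAP 5.4.5 covers laboratory data and vital signs only, and SAP Table 10 has no diary column.

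**The concern.** The diary starts at Visit 1, two to four weeks before dosing, so screening entries exist and a flat four-week look-back from Week 2 reaches into them. The Week 2 NC value is then partly a baseline value, and the week that defines baseline is counted again in the post-baseline score.

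The value has three possible uses:

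- SAP 4.5.2.3 summarises secondary endpoints at each visit up to Week 24.
- The imputation steps in SAP 4.4.1.2 use values at all applicable visits through Week 24, without defining applicable.
- It may be a candidate for the worst value carried forward after rescue.

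Because the truncation and completeness rules stand only under TSS and smell, a programmer can follow the text and give one diary item two windows. The unqualified mention of the previous visit leaves a second choice open, this time for the Week 24 TSS and smell scores.

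**Working it through.** **Inputs.** Visit days are from the protocol schedule: Week 2 = Day 15, Week 4 = Day 29, Week 16 = Day 113, Week 24 = Day 169, each ±3 days. Visit 1 falls between Day -28 and Day -14. Day 1 is first dose and there is no Day 0. The window rules are those quoted above. No figure in the plan has to be reproduced for this point.

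**1. Pre-treatment days in the NC window.** For a visit on Day d, the 28 days before it contain d − 1 days from Day 1 onward, so 28 − (d − 1) precede Day 1.

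- Week 2, Day 15: 28 − 14 = 14 (Day -14 to Day -1), including all 7 baseline days.
- Week 2, Day 12: 28 − 11 = 17. Day 18: 28 − 17 = 11. The count of 17 needs a Visit 1 on or before Day -17.
- Including the visit day in a Day 15 window gives 13 instead of 14.
- Week 4, Day 29: 28 − 28 = 0. Day 26: 28 − 25 = 3.
- Week 24, Day 169: the window is Days 141 to 168, with none.

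The Day 1 entry is also likely to be pre-dose. It is a morning entry (protocol 8.1.4) reflecting the past 24 hours (protocol 8.1.2), and dosing follows the visit assessments (schedule footnote c). Counting it gives 15 of 28 for a Day 15 visit.

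**2. Dilution at Week 2.** Assume a complete diary, a pre-treatment mean B equal to baseline, and a constant mean P from Day 1. For Day 15:

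Week 2 score = (14B + 14P)/28, so change as scored = (P − B)/2.

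With B assumed to be 2.4:

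| P | True change | Change as scored |
|---|---|---|
| 2.0 | −0.4 | −0.2 |
| 1.6 | −0.8 | −0.4 |
| 1.2 | −1.2 | −0.6 |

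In general the share kept is (d − 1)/28: 11/28 = 39% for Day 12, 14/28 = 50% for Day 15, 17/28 = 61% for Day 18.

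**3. The two sections side by side, with visits on schedule and only scheduled visits counted.**

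| Visit | NC as written | TSS and smell as written |
|---|---|---|
| Week 2 | Day -14 to Day 14 | Days 2 to 15 |
| Week 4 | Days 1 to 28 | Days 16 to 29 |
| Week 24 | Days 141 to 168 | Days 141 to 168 |
| Minimum entries | none stated | 50% of window days |

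Congestion is a component of TSS, so the same item is averaged over two different periods at Weeks 2 and 4. At Week 24 the windows agree, but only TSS and smell have a completeness rule.

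**4. Week 24 truncation for TSS and smell.** Week 16 to Week 24 is 169 − 113 = 56 days, and at least (169 − 3) − (113 + 3) = 50. On the scheduled-visit reading the window is always the full 28 days.

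If an unscheduled visit on Day u counted as the previous visit, truncation would require 169 − u < 28, that is, u of 142 or later:

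| Unscheduled visit | Window | Entries needed at 50% |
|---|---|---|
| Day 141 or earlier | 28 days | 14 |
| Day 155 (Week 22 site injection) | Days 156 to 169, 14 days | 7 |
| Day 162 | 7 days | 4 |
| Day 166 | 3 days | 2 |

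**The case against.** The strongest reply on Week 2 is that 4.4.2.1 ties TSS and smell to the NC approach, so one rule was probably meant for all diary scores. Applied to NC, the truncation gives Days 2 to 15 with no screening entry. That is a plausible intent, but it is not written: 4.4.1.1 neither states the truncation nor refers forward to it, and protocol 8.1.2 matches the flat version.

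The reply on impact largely stands. The observed Week 24 NC window is clean, the primary endpoint is based on NPS, no hypothesis is tested, and dilution understates early benefit. The worst-value route is also limited. The steps in SAP 4.4.1.2 already admit baseline as a worst value, so a blend of screening and treated days would rarely be the worst. SAP Table 3 falls back on baseline only when all post-baseline values are missing. On that wording the Week 2 value could be carried to Week 24 for someone rescued between Weeks 2 and 4.

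On Week 24, a reader might infer that any unscheduled visit cuts the TSS and smell window. The documents do not support that. The preceding sentence names scheduled visits, the rule has an obvious use for the 14-day gaps at Weeks 2 and 4, and where SAP 5.4.5 wants unscheduled measurements used it says so, without listing diary scores. Even on the wide reading, visits up to Day 141 change nothing.

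A reader might also infer that truncation would favour the drug by removing bad days before a deterioration visit. That is not shown. Site injections have no stated link to symptoms, symptoms may stay bad after a deterioration visit, and deterioration treated with systemic corticosteroids or surgery is handled as rescue.

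**Conclusion.** The Week 2 part holds on the text. The stated NC rule puts 14 of 28 pre-treatment days into the average for a Day 15 visit (11 to 17 across the visit window). It roughly halves the Week 2 NC change if screening and treated levels are each steady and the diary is complete. The by-visit table is directly affected. Any effect on the Week 24 NC estimate can come only through imputation, as a predictor or a worst-value candidate, and its size cannot be fixed from the documents.

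The mismatch between 4.4.1.1 and 4.4.2.1 also holds: different Week 2 and Week 4 windows for the same diary item, and no completeness minimum for post-baseline NC.

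The Week 24 TSS and smell part is an ambiguity only. It matters if visits are read to include unscheduled ones and such a visit falls fewer than 28 days before Week 24. The scheduled-visit reading is the more natural one. The point is worth correcting because a stated rule gives a wrong by-visit value, but it does not undermine the observed Week 24 results.

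**What to change.** Put one rule in SAP 4.4.1.1 for NC, smell and TSS, and replace the separate text in 4.4.2.1 with a reference to it:

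- Average the 28 days up to the scheduled visit, starting no earlier than the day after the previous scheduled visit. For Week 2 this means the day after Visit 2, Day 2. Starting on the day of first dose would let in a morning entry that reflects the hours before dosing.
- State that unscheduled visits do not change the window.
- Require at least 50% of window days to be non-missing, for NC as well.
- Say whether the visit day counts. The truncation sentence includes it; the 28-day sentence reads as if it does not.

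Because protocol 8.1.2 carries the flat NC rule, record the change in SAP Appendix 2 (changes to protocol-planned analyses). The cost is SAP wording and matching programming. No new data are needed.
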